8.1 Screening

Screening

All participants must provide signed ICFs prior to performing any study specific procedures. Screening assessments to confirm eligibility should be performed as per the schedule of assessments detailed in Table 8-1. Participants will be evaluated against all study inclusion and exclusion criteria and safety assessments which must be completed within 28 days prior to the start of study treatment (C1D1), with the exception of the local serum pregnancy test (for women of childbearing potential) which must be conducted and confirmed as negative within 72 hrs prior to the start of study treatment. Laboratory parameters may be retested within the 28-day screening period. If the repeat value remains outside of the specified ranges, the participant will be considered a screen failure.

An individual participant may only be re-screened once for the study. A new ICF will need to be signed if the investigator chooses to re-screen the participant. Any re-screened participant should receive a new participant No., and the original participant number must be noted on the Re-Screening CRF. All required screening activities must be performed when the participant is re-screened for participation in the study.

8.1.1 Eligibility screening

Following registering in the IRT for screening, participant eligibility will be checked once all screening procedures are completed. The eligibility check will be embedded in the IRT system. Please refer and comply with detailed guidelines in the IRT manual.

8.1.2 Information to be collected on screening failures

Participants who sign an informed consent form and subsequently found to be ineligible prior to administration of study treatment (C1D1) will be considered a screen failure. The reason for screen failure should be recorded on the appropriate Case Report Form (CRF). The demographic information, informed consent, and Inclusion/Exclusion pages must also be completed for screen failure participants. No other data will be entered into the clinical database for participants who are screen failures, unless the participant experienced a serious adverse event during the screening phase (see Section 10.1.3 for reporting details). If the participant is screen failed or will not be treated, the IRT is to be notified as soon as possible that the participant was not enrolled.

8.2 **Participant demographics / other baseline characteristics**

Demographics and other baseline characteristics data to be collected on all participants include:

- Disease history, including date of diagnosis, confirmation of MDS diagnosis, IPSS-R risk classification for MDS participants at time of screening, prior antineoplastic therapies. Calculation of IPSS-R risk score for MDS participants and should be done based on the hematology values obtained at screening.
- Relevant prior antineoplastic therapies and all concomitant medications and medical procedures

• Blood transfusions (RBC/platelets) **administered within 16 weeks** before the first dose is administered

Other assessments will be completed for the purpose of determining eligibility for inclusion in the study as reported in Table 8-1.

Assessments to be performed at screening include:

- After all study ICFs are signed the participant will be registered with the IRT
- Inclusion/exclusion criteria
- Medical history/current medical conditions
- Disposition
- Physical examination
- ECOG Performance Status, body height, weight, vital signs (blood pressure (supine position preferred when ECGs are collected) and pulse, and body temperature).
- Laboratory hematology, blood chemistry, coagulation, urinalysis (dipstick and sediment), serum pregnancy test for women of child-bearing potential, thyroid function, cytogenetics, virology hepatitis B and C, HIV serology (only if required per local regulation)
- Triplicate 12-lead central ECG
- Bone marrow aspirate (BMA) or biopsy will be performed locally to establish the diagnosis. Cytogenetics will be performed locally as per local standard. If a bone marrow aspirate or biopsy was conducted during the regular work-up of the participant and fall within the 28 days prior to start of treatment (although prior to signing main study ICF), it may be considered as the baseline assessment for the study.

Bone marrow and peripheral blood pathology specimens (i.e. bone marrow slides, bone marrow biopsy block if applicable, peripheral blood smears) prepared locally for establishing the MDS diagnosis at the time of screening, should be sent to the Novartis designated central laboratory for storage. A copy of the corresponding pathology reports should be collected and sent to the Novartis designated central laboratory for storage. Central morphology review of the pathology specimens may be performed, if deemed necessary.

- Blood sample for Cytokines
- Adverse events

Authorities. Investigators will have the discretion to record abnormal test findings on the medical history CRF whenever in their judgment, the test abnormality occurred prior to the informed consent signature. Significant new findings that begin or worsen after informed consent must be recorded on the AE page of the participant's eCRF.

After all applicable study ICFs are signed, the participant will be registered in the IRT system.

8.3 Efficacy

8.3.1 Efficacy assessments

Disease response will be assessed locally by the investigator in all participants (MDS) according to modified IWG for MDS and WHO criteria (Cheson et al 2000, Cheson et al 2006, Arber et al, 2016, Platzbecker 2019). Response criteria are described in Table 8-2.

Investigators will assess and document response/progression at each time point as per the visit schedule. For efficacy analyses, baseline assessment is defined as the last non-missing assessment on or before the date of sabatolimab.

In addition, the hematological improvement per modified IWG-MDS criteria (Cheson et al 2006) will be assessed in all enrolled participants to report specific hematologic improvement (HI) of cytopenias in the three hematopoietic lineages: erythroid (HI-E), platelet (HI-P), and neutrophil (HI-N).

Response category	Definition [#]
Complete remission (CR)	Bone marrow:
	<= 5% blasts with normal maturation of all cell lineages. (Note: Persistence of dysplasia will be noted but does not preclude achievement of complete remission [CR])
	Peripheral blood:
	1. Hgb $\geq 10 \text{ g/dl}$ AND
	2. Platelets $\geq 100*10^9$ /L AND
	3. Neutrophils $\geq 1.0*10^9$ /L AND
	4. Blasts 0%
	(Note: the participant must not receive RBC or platelet transfusions, myeloid growth factor within 2 weeks before this disease assessment)
marrow Complete remission (mCR)	Bone marrow:

Table 8-2Modified response classification per IWG-MDS criteria (Platzbecker et
al 2019, Cheson et al 2006, Cheson et al 2000)

Response category	Definition [#]
	<= 5% blasts and blast count decrease by \geq 50% compared to baseline
	Peripheral blood/transfusion: Marrow CR may be achieved with or without improved blood counts or with or without transfusions
Partial remission (PR)	All CR criteria except
	Bone marrow: $\geq 50\%$ decrease from baseline in blasts in bone marrow AND blast count in bone marrow $> 5\%$
Stable Disease (SD)	Failure to achieve at least PR, but no evidence of progression for >8 weeks
Relapse from CR	Only in participants with a CR
	At least 1 of the following criteria is met: [in absence of another explanation not due to MDS, such as acute infection, bleeding, hemolysis, etc. Note that observation of peripheral blasts is not a sufficient criterion for relapse. However in that case, a bone marrow examination should be made to determine whether relapse has occurred]
	1. Return to baseline bone marrow blast percentage
	2. Decrease of $\geq 50\%$ from maximum remission/response*** levels in neutrophils AND neutrophils $<1.0*10^{9}/L$. Note: neutrophils counts during periods of active infection will not be considered in determining the maximum
	3. Decrease of \geq 50% from maximum remission/response*** levels in platelets AND platelets < $100*10^{9}/L$
	4. Decrease from maximum remission/response*** levels in Hgb concentration by ≥ 1.5 g/dL AND Hgb < 10 g/dL
	5. Becoming transfusion dependent**
Disease progression	At least 1 of the following criteria is met:

Response category	Definition [#]
	[in absence of another explanation not due to MDS, such as acute infection, bleeding, hemolysis, etc. Note that observation of peripheral blasts is not a sufficient criterion for progression. However in that case, a bone marrow examination should be made to determine whether relapse has occurred]
	Bone marrow according to the number of blasts of the participant at baseline:
	1. Less than 5% blasts at baseline : \geq 50% increase in blasts over baseline to > 5% blasts
	2. 5% - < 10% blasts at baseline : \geq 50% increase over baseline to > 10% blasts
	3. $10\% - < 20\%$ blasts at baseline : $\ge 50\%$ increase over baseline to $> 20\%$ blasts.
	Participants with more than 20% of blasts will be considered to have transformation to acute leukemia per 2016 WHO classification (Arber et al, 2016)
	Peripheral blood:
	1. Decrease of $\geq 50\%$ from maximum remission/response*** levels in neutrophils AND neutrophils < $1.0*10^9/L$. Note: neutrophils counts during periods of active infection will not be considered in determining the maximum
	2. Decrease of \geq 50% from maximum remission/response*** levels in platelets AND platelets < $100*10^9/L$
	3.Reductionfrommaximumremission/response***levelsinHgbby2g/dLANDHgb $10g/dL$
	Becoming transfusion dependent**
	Occurrence of acute leukemia, or extramedullary leukemia per investigator's judgement

Modified Hematologic Improvement per IWG-MDS criteria (Cheson et al 2006)

Response category	Definition [#]
HI category	Definition [#] (HI must last at least 8 weeks)
Erythroid response (HI-E) (pretreatment*, <11 g/dL)	1. Hgb increase from baseline by \geq 1.5 g/dL, in at least 2 consecutive Hgb measurements and maintained over at least 8 weeks
	2. Relevant reduction from baseline of units of RBC transfusions by an absolute number of at least 4 RBC transfusions/8 weeks compared with the pre-treatment transfusion number in the previous 8 weeks. Only RBC transfusions given for a Hgb of < 9 g/dL pre- treatment will count in the RBC transfusion response evaluation.
Platelet response (HI-P) (pretreatment*, <100 x 10 ⁹ /L)	1. Absolute increase from baseline of \geq 30 x 10 ⁹ /L for participants starting with $>$ 20 x 10 ⁹ /L platelets
	2. Increase from baseline from $< 20 \times 10^9$ /L to $> 20 \times 10^9$ /L and by at least 100% for participants starting with $< 20 \times 10^9$ /L platelets
Neutrophil response (HI-N) (pretreatment*, <1.0 x 10 ⁹ /L)	At least 100% increase and an absolute increase from baseline of $> 0.5 \text{ x } 10^9/\text{L}$

[#]If not defined otherwise, all of the criteria apply. Words that are written in italics highlights the modifications from the IWG criteria described in the reference publications.

**Pretreatment counts correspond to the baseline (not influenced by transfusions)*

**Definition of transfusion dependence and independence for red blood cells (RBC) and/or platelets are described below.

***maximum remission/response levels correspond to the best values reported in post baseline.

Transfusions Status Definitions for RBC/platelets

Transfusions for intercurrent diseases not due to study indication (e.g. bleeding, surgical procedure, hemolysis, infections) should not be taken into account for the following:

Transfusion dependence:

1. At baseline: participants having received ≥ 3 units of transfusion within the 8 consecutive
weekspriortobaseline.2. Post-baseline: participants having received ≥ 3 units of transfusion within any 8 consecutive
weeks during the course of the study ≥ 3 units of transfusion within any 8 consecutive

Transfusion independence:

1. At baseline: participants having received 0 units of transfusion within the 8 consecutive weeks prior to baseline.

2. Post-baseline: participants having received 0 units of transfusion within any 8 consecutive weeks during the course of the study.

Response assessment will be performed by investigator according to the assessment schedule depicted in Table 8-1. Moreover, participants can be assessed for disease response (bone marrow assessment, hematology, transfusion) at any time if clinically indicated as an example if there is a clinical suspicion of progression/relapse, in particular after a participant has achieved a CR.

Bone marrow assessments will be performed at screening and pre-dose on C3D1. From C7D1, bone marrow assessments will be performed every 3 cycles until C13D1 (C7D1, C10D1, C13D1), then every 6 cycles until C25D1 (C19D1 and C25D1) and thereafter every 12 cycles (C37D1, C49D1 etc.) and as clinically indicated during the treatment period.

Hematology assessments will be performed at screening, pre-dose on D1, D8 and D22 of Cycles 1 and 2, and thereafter pre-dose on D1 and D8 of each cycle until end of treatment.

Bone marrow and peripheral blood pathology specimens (i.e. bone marrow aspirate slides, bone marrow biopsy block if applicable, peripheral blood smears) prepared locally for the disease response assessment, should be sent to the Novartis designated central laboratory for storage. This includes specimens taken during the regular work-up of the participant and used as baseline assessment for the study as mentioned in Section 8.2. A copy of the corresponding pathology reports should be collected and sent to the Novartis designated central laboratory for storage. Central morphology review of the pathology specimens may be performed, if deemed necessary. For China only: Storage of the above pathology specimens and reports in a Novartis designated laboratory will be performed, if adequate approval has been obtained from all relevant Chinese authorities.

Participants who discontinue treatment for reasons other than documented disease progression, death, lost to follow-up, or withdrawal of consent, will enter the efficacy follow-up phase.

In the efficacy follow-up phase, hematology assessments must continue to be performed every 3 months, response should be assessed at least every 12 months, and bone marrow assessment should be done at least every 12 months thereafter per Table 8-1, or as clinically indicated any time in case disease progression is suspected. Further information about blood transfusions will be continuously collected throughout the efficacy follow-up period.

The efficacy follow-up period will last until participant's documented disease progression (per IWG criteria Table 8-2), death, lost to follow-up, or withdrawal of consent, or the end of the study whichever comes first. Post-treatment antineoplastic therapies, including HSCT, will continue to be captured during survival follow-up (see Section 9.1.1.3 and Table 8-1).

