Hospitalization is required at Cycle 1 from Day 1 to Day 3 for participants participating to Safety run-in (cohorts 1 and 2) in order to monitor closely the chemistry parameters, in particular to detect occurrence of TLS, (see Section 6.5.4.2), and thereafter at the discretion of the investigator. Study treatment will be administered in cycles with a planned duration of 28 days, and study treatment may continue until the participant experiences disease progression (Fenaux et al 2014) or unacceptable toxicity.

In each 28 day-cycle:

- azacitidine will be administered intravenously or subcutaneously at 75 mg/m² on Days 1 to 7 (or, at discretion of the investigator on Days 1-5 and Day 8-9), during Safety run-in (Part 1) and Expansion (Part 2).
- venetoclax will be administered orally at 400 mg daily for 14 consecutive days, during Safety run-in (Part 1) and Expansion (Part 2). No ramp-up of venetoclax is necessary in this trial (see Section 4.3).
- sabatolimab will be administered intravenously at 400 mg (during Safety run-in cohort 1) or 800 mg (during Safety run-in cohort 2 and Expansion) on Day 8 (Q4W).

Novartis	Confidential	Page 32 of 143
Amended Protocol Version 02 (Clean)		Protocol No. CMBG453B12203

At any time during the study, participants unable to tolerate one or two of the study treatment drugs, may continue study treatment with only the tolerated drug(s). Use of prophylactic antibiotics as per institutional guidelines is mandatory at Cycle 1; and thereafter prophylactic antibiotics may be used at the physician's discretion. Prophylactic antifungals as per institutional guidelines may be used at the physician's discretion at anytime. See Section 6.2.1.1, regarding the adjustment of dose for venetoclax in case of concomitant use of antibiotics and/or antifungals.

After the end of study treatment, all participants must be followed for adverse events (AEs) for 30 days; in addition, follow-up for AEs will be conducted for 150 days following the last dose of sabatolimab. All participants who discontinue study treatment will enter a long-term follow-up (for efficacy and/or survival status) as described in the study flow diagram below (Figure 3-2) and outlined in Section 9.1.

Figure 3-2 Study flow

The study flow is comprised of 3 study periods see (Figure 3-2): Pre-treatment (Screening), treatment and follow-up.

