6.1.1 Investigational and control drugs

Investigational/ Combination Drug (Name and Strength)	Strength	Pharmaceutical dosage form and route of administration	Supply Type	Sponsor (global or local)
Sabatolimab	400 mg/4 ml	solution in vial for i.v. infusion	solution in vial Open Label for i.v. infusion	
Venetoclax	100 mg and/or 50 mg and/or 10 mg	tablet for oral use	Open Label	Sponsor (global/local)
Azacitidine*	100 mg / vial	powder for suspension for injection or powder for solution for infusion for subcutaneous use or intravenous use	Open Label	Sponsor (global/local)

Table 6-1Study Treatment

*formulation for generic azacitidine as approved by local regulations

Sabatolimab

Sabatolimab will be administered at a dose of 400 mg Q4W (Safety run-in (Part 1) cohort 1) or 800 mg Q4W (Safety run-in (Part 1) cohort 2 and Expansion (Part 2)) via i.v. infusion over 30 minutes on Day 8 of every 28-day cycle.

If the alternative schedule is selected for azacitidine by the investigator, azacitidine and sabatolimab will be given on the same day (Day 8 of the 28-day cycle). Azacitidine should be administered first, followed by sabatolimab.

Further instructions for the preparation, dispensation and administration of sabatolimab are described in the Pharmacy Manual.

Venetoclax

Venetoclax film-coated tablets should be administered at a dose of 400 mg orally or corresponding reduced dose for concomitant use with P-gp inhibitors or moderate or strong CYP3A4 inhibitors (see Table 6-2 and Venclexta[®] (Venclexta[®] (Venetoclax) USPI (2020)), once a day, from C1D1 to C1D14 during the 28-day cycle. Participants should be instructed to

swallow the tablets whole (tablets should not be crushed or broken), with water, at approximately the same time each day. The tablets should be taken with a meal (ideally at breakfast). No ramp-up for venetoclax is necessary, See Section 3, Section 4.3 and Section 6.5.4.2.

A reduced dose of venetoclax per day for concomitant use with P-gp inhibitors or moderate or strong CYP3A4 inhibitors (see Table 6-2 and Venclexta[®] (Venclexta[®] (Venetoclax) USPI (2020)) is necessary. In particular, many antifungals (e.g. posaconazole) and antibiotics, frequently used for prophylaxis or treatment of infection, are strong or moderate CYP3A4 inhibitors and their use should lead to dose adjustment of venetoclax as indicated in Table 6-2.

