- The date of the event (visit date, onset date of an event, assessment date etc.) reference start date + 1 if event is on or after the reference start date;
- The date of the event (visit date, onset date of an event, assessment date etc.) reference start date if event precedes the reference start date.

The reference start date for safety assessments (e.g. adverse event onset, laboratory or ECG assessment, vital sign measurement etc.) is the start of study treatment. The same reference start date will be used for efficacy (e.g. response assessment, time-to-event endpoints) and patient-reported outcomes (PRO).

The study day will be displayed in the data listings. If an event starts before the reference start date, the study day displayed on the listing will be negative.

Time unit

A year length is defined as 365.25 days. A month length is 30.4375 days (365.25/12). If duration is reported in months, duration in days will be divided by 30.4375. If duration is reported in years, duration in days will be divided by 365.25.

Baseline

For efficacy evaluations and PROs, the last non-missing assessment, including unscheduled assessments on or before the date of start of study treatment is taken as "baseline" value or "baseline" assessment.

For safety evaluations, the last available assessment including unscheduled assessments on or before the date of the start of study treatment is taken as "baseline" assessment. If participants have no value as defined above, the baseline result will be missing.

Windows for multiple assessments

Time windows will be defined for descriptive summary of ECOG and PRO data (EORTC QLQC30, by visit and the longitudinal data analysis. If more than one assessment is available in the same time window, the assessment closest to the planned date will be considered. If two assessments are obtained with the same time difference compared to the scheduled visit day, the assessment obtained prior to the visit will be considered. Data obtained at the end of treatment visit will be classified as other assessment in the corresponding time window. For participants who discontinue treatment for reasons other than progressive disease, withdraw consent or death, EORTC QLQ-C30 5L will continue being collected every 6 months during this follow-up period until disease progression.

Table 4-1	Time windows	for PRO	and ECOG data

Assessment	Target day of assessment	Time Window Definition
Baseline	On or before Study Day 1[a]	≤ Study Day 1

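### Protocol 8.3.1 dates the efficacy baseline to sabatolimab (Cycle 1 Day 8), so count-based hematologic improvement is, read literally, judged against on-treatment counts; Table 8-2 and the SAP use a pre-treatment baseline

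*Protocol*

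**What the plan says.** Protocol 8.3.1 (Efficacy assessments) tells investigators to document response at each visit, then states that for efficacy analyses "baseline assessment is defined as the last non-missing assessment on or before the date of sabatolimab".

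The dosing calendar puts the other two drugs first. Under Protocol Section 3, "azacitidine will be administered intravenously or subcutaneously at 75 mg/m² on Days 1 to 7", with an alternative of Days 1-5 and 8-9. Under Protocol 6.1.1, venetoclax is taken "once a day, from C1D1 to C1D14 during the 28-day cycle". Sabatolimab is given on Day 8 of each cycle.

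On sampling, 8.3.1 says: "Hematology assessments will be performed at screening, pre-dose on D1, D8 and D22 of Cycles 1 and 2". For marrow: "Bone marrow assessments will be performed at screening and pre-dose on C3D1", with the next planned sample at C7D1.

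Table 8-2 defines HI as change from baseline and restricts each lineage to participants below an entry value: hemoglobin <11 g/dL, platelets <100 x 10⁹/L, neutrophils <1.0 x 10⁹/L. Its footnote reads: "Pretreatment counts correspond to the baseline (not influenced by transfusions".

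SAP Section 4 differs from 8.3.1. There the last non-missing efficacy assessment "on or before the date of start of study treatment is taken as" the baseline value, and the start of study treatment is the first non-zero dose of any of the three drugs. SAP Section 3 lists two departures from the protocol, the primary CR analysis and the patient-reported outcomes. The baseline is not among them.

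**The concern.** Protocol 1.1 describes the safety profile of azacitidine plus venetoclax as mainly myelosuppression. A reference count taken a week into that doublet may sit below the participant's true pre-treatment level, and recovery towards that level could then be scored as improvement.

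The SAP's better definition does not clearly repair this. Under SAP 2.5.1.2 the investigator enters the response categories in the eCRF, and the sponsor derives best overall response from those entries. HI counts if there is at least one determination of it and nothing better. No step recalculates HI from laboratory counts, so the SAP baseline need not reach an HI entry.

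What is at stake is the overall response rate (HI or better) and the date on which a response is taken to begin. SAP 1.2 keeps all objectives except fatigue in the abbreviated report, so both will still be reported.

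**Working it through.** **1. Which value becomes baseline.** I take the date of sabatolimab in 8.3.1 to mean its first dose. Counts are scheduled at screening, C1D1 pre-dose and C1D8 pre-dose, so the last one on or before first sabatolimab is C1D8. By then venetoclax has been given on Days 1-7, and azacitidine on Days 1-7 or, on the alternative schedule, Days 1-5. Under the SAP the baseline count is C1D1 pre-dose or earlier.

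**2. Which criteria use it (Table 8-2).**
- CR: absolute thresholds only, no baseline term. The design rule (36 CR of 70) is therefore untouched. It reproduces as stated: posterior median 51.4%, posterior probability of CR rate above 39% equal to 0.983, power 0.80 at 39/70.
- mCR, PR and marrow progression: baseline marrow blasts. With planned marrows at screening and C3D1, the reference is the screening marrow under either definition. An unscheduled marrow in Days 1-8 would be the exception.
- Blood-count progression: compared with the best post-baseline value, not the baseline count. The baseline date matters only through which early values count as post-baseline.
- HI in the three lineages: change from the baseline count, and entry values that also use baseline.

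**3. How the HI threshold moves.** Let b be the baseline count. The later value needed is:
- HI-P (b above 20): b + 30
- HI-N: the larger of 2b and b + 0.5 (the absolute rise must exceed 0.5)
- HI-E: b + 1.5

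The documents give no Day 1 to Day 8 change, so the starting values and falls below are assumptions.

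| Day 1 value | No fall | 10% fall | 25% fall | 50% fall |
|---|---|---|---|---|
| Platelets 60 | 90 | 54+30 = 84 | 45+30 = 75 | 30+30 = 60 |
| Neutrophils 0.9 | 1.80 | 2×0.81 = 1.62 | 2×0.675 = 1.35 | 0.45+0.5 = 0.95 |
| Platelets 110 | not eligible | 99+30 = 129 | 82.5+30 = 112.5 | 55+30 = 85 |

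For hemoglobin 9.0 g/dL on Day 1, the value needed is 10.5 with no fall, and 10.0, 9.5 or 9.0 after a fall of 0.5, 1.0 or 1.5 g/dL.

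At a 50% fall, returning to the Day 1 platelet count of 60 would meet the HI-P threshold. A participant at 110, ineligible on Day 1, becomes eligible and could qualify at 85.

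**4. Single example.** Platelets 60 on Day 1, 40 on Day 8, then 75 sustained for the 8 weeks that Table 8-2 requires: 75 − 40 = 35 (HI-P met); 75 − 60 = 15 (not met).

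**5. What one reclassified participant does to ORR.** At planned cohort sizes: 1/6 = 16.7 percentage points at 400 mg, 1/12 = 8.3 points at 800 mg.

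**The case against.** The sentence in 8.3.1 opens by limiting itself to efficacy analyses, so it is not an outright instruction to investigators. Sites score HI from Table 8-2, whose wording points to pretreatment counts. Protocol 8.2 likewise accepts as the baseline marrow a sample taken before the start of treatment. A site might well have used Day 1 throughout, and nothing in the documents shows one using Day 8. This stands: use of Day 8 is an inference from the text. But 8.3.1 gives the only dated baseline for counts in the response section and directly follows the instruction to assess response, so sites could reasonably differ.

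The effect on ORR is also limited. CR, mCR and PR all outrank HI in best overall response, and HI must last 8 weeks. ORR changes only for a participant who has HI and nothing better, and who crosses the threshold only because the Day 8 count was lower. That stands too. So does the point that recruitment stopped after the run-in, leaving ORR descriptive in about 18 planned participants with no decision attached.

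A reader might infer more: that progression and PR are distorted as well, that every participant's result is affected, or that duration of response is inflated. The documents do not support these. Step 2 shows why progression and PR keep their references. Having a Day 8 count exposes a participant to the definition but need not change any outcome. For duration, an earlier HI could lengthen an individual's response, while added HI-only responders could shorten the median, so the direction is not settled.

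**Conclusion.** The inconsistency is real and confined to count-based HI. Protocol 8.3.1 places the reference count at C1D8, Table 8-2 and the SAP place it before treatment, and the difference is not declared. If counts fall between Day 1 and Day 8, a literal reading of 8.3.1 makes HI easier to reach. ORR can then rise through participants whose best response is HI only, and the onset of response can shift. The size cannot be estimated from the documents; the illustrations rest on assumed falls of 0 to 50% (0 to 1.5 g/dL for hemoglobin). The result also assumes that at least some investigators followed 8.3.1 literally. The primary CR endpoint and the design figures are not affected. It is worth correcting because the remedy is cheap and the cohorts are small enough for one reclassified participant to show.

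**What to change.** Amend Protocol 8.3.1 so that the efficacy baseline is the latest available assessment on or before the first dose of any of the three drugs, matching SAP Section 4. Tell sites that this baseline governs HI, including the three entry values. Before database lock, check HI entries against counts taken before the first C1D1 dose, or re-derive HI from them. Record the difference between protocol and SAP in SAP Section 3. No matching checks on PR or progression are needed.

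The counts are already collected, so the cost is a modest amount of query or programming work. Protocol 14.1 requires a formal amendment with ethics and, where applicable, health authority approval. According to the SAP introduction, even the recruitment halt was not put into an amendment. If one is impractical now, the re-derivation specified in the SAP plus the Section 3 entry is enough.
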